- Blood sampling for hematology and biochemistry (APPENDIX II)
- Blood sampling with Analysis Kit in week 3-4 and 9-12 only in patients who have given informed consent - part 3 for translational medical investigations (TraFo-Project)
- Blood sampling with Analysis Kit afterwards every 3 months in everolimus/ribociclib cohort only nse
- Tumor evaluation every 12 weeks (in the everolimus/ribociclib cohort together with blood sampling for CTC count)
- Quality of life assessment: EORTC QLQ-C30 and EORTC QLQ-BR23
- Tablet count, additional dispense of everolimus/ribociclib if necessary
- Pregnancy test (eribulin cohort only)
- Survival

Conclusion Visit of the Treatment Period

As soon as possible after disease progression, completion or premature discontinuation of protocol treatment or respectively 12 months after inclusion:

- Vital signs
- Physical examination
- Standard 12-lead ECG
- Adverse events
- Concomitant medication
- Documentation of end of protocol treatment and planned therapy after end of protocol treatment
- Blood sampling for hematology and biochemistry
- Blood sampling with Analysis Kit
- Quality of life assessment: EORTC QLQ-C30 and EORTC QLQ-BR23
- Tablet count, collection of unused everolimus/ribociclib
- Pregnancy test (eribulin cohort only)
- Survival
- Reminding patient of the follow-up procedures planned

Follow up assessments

Between 2 and 4 weeks after Conclusion Visit of the Randomized Treatment Period and then every 3 months:

- Adverse events which are \geq grade 3 NCI CTCAE and/or serious
- Concomitant medication
- Survival

Objectives and Endpoints of Clinical Trial

Primary objective:

Everolimus/Ribociclib cohort (DIVa)

The primary objective is to investigate the clinical efficacy of everolimus/ribociclib (as assessed by the CTC clearance rate) in combination with endocrine therapy in postmenopausal patients with hormone-receptor positive, HER2-negative metastatic breast cancer and persisting only HER2-negative circulating tumor cells (CTCs).

Eribulin cohort (DIVb)

The primary objective is to investigate the clinical efficacy of eribulin (as assessed by progression-free survival, PFS) both in patients with HER2-negative, hormone-receptor positive metastatic breast cancer and indication to chemotherapy and triple-negative metastatic breast cancer both with persisting only HER2-negative CTCs.

Secondary objectives:

In General

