
 • Progression-free survival (PFS), defined as time interval from date of recruitment until progressive disease (PD) or death from any cause, whichever comes first (as defined by RECIST guideline version 1.1). • Dynamic of CTCs: changes in CTC counts from baseline numbers (start of treatment) to the time of first radiological tumor evaluation after about 12 weeks, and every 12 weeks thereafter until progression • Levels of pS6 at baseline, at first radiological tumor assessment after about 12 weeks, and at the time of progression • Change in the activation of the PI3K/Akt/mTOR-pathway in CTCs as assessed by longitudinal comparisons (at baseline, after 12 weeks, at time of progression) • Estrogen-receptor 1 (ESR-1) mutations in CTCs at baseline, after 12 weeks and at time of progression 	
 • Dynamic of CTCs: changes in CTC counts from baseline numbers (start of treatment) to first (6 weeks) and second (12 weeks) control visit as well as the time of progression or end of treatment. • New metastasis-free survival (nMFS), defined as time from recruitment to death or progression due to appearance of a new metastasis, whichever comes first. If a patient has not had an event, nMFS is censored at the date of last adequate tumor assessment.

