Based on these data the aims of this translational research project are to determine the predictive values of the detection of aberrant 53BP1 signals on CTCs and genetic alterations in BRCA1 in peripheral blood samples as potential biomarkers for responsiveness to therapy with Eribulin in patients with triple negative, metastatic breast cancer and persisting HER2-negative CTCs. In addition, the dynamic of 53BP1 signals on CTCs will be assessed by longitudinal comparisons before, during, and after treatment, and the suitability of the different measures for assessing therapy efficacy will be evaluated.

Qualitative and quantitative immunofluorescence microscopic detection of nuclear 53BP1 foci in immortalized and primary cells from various human cell types has been established in the Section of Gynecological Oncology, Department of Obstetrics and Gynecology, Ulm University (see e.g. Volcic et al. 2012). The protocol will be adapted for use in the Cell Search® System (Cell Search® Epithelial Cell, Cell Search® CXC vs. Profile Kit; choice of fluorophore; cut-offs regarding signal intensity vs. foci numbers; exposure/integration time etc.) using blood samples spiked with well-described BRCA-mutated and/or TNBC cell lines (HCC1937, MDA-MB-436, MDA-MB-468) following guide lines established with γ H2AX detection on CTCs (Wang et al. 2010).

The optimized protocol will be applied to blood samples (10 ml CellSave Preservative Tubes, Veridex Inc.) collected from TNBC patients during the Randomization visit, if CTCs ($\geq 1 / 7.5$ ml blood) with HER2-negative status were detected in blood samples retrieved during the Screening visit. Additional blood samples will be collected 0, 6, and 12 weeks after treatment start with Eribulin. CTC enrichment and enumeration from samples in CellSave tubes will be performed following the instructions by Veridex LLC. CTCs, captured from peripheral blood by EpCAM-antibody and identified by cytokeratin8/18/19-positivity and CD45-negativity, will be analysed for 53BP1 signals within the DAPI-stained nucleus by use of corresponding antibody dilutions (according to optimized protocol). Homogeneous, diffuse 53BP1 staining will be categorized into negative (0), weak (1+), moderate (2+), and strong (3+) staining analogous to HER2-specific immunofluorescence. Discrete, focal 53BP1 signals will be scored per nucleus and positivity defined by use of the cut-off level established in the optimized protocol.

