9.1 Evaluation during Treatment Period

In General

With the exception of the blood samplings for circulating tumor cells and translational medical investigations, assessment of adverse events, survival, quality of life and tablet count all procedures performed during treatment period are part of the clinical routine usual in metastatic breast cancer.

Scheduled Control Visits

For all patients there is a visit every 2 – 4 weeks for Everolimus/ribociclib cohort and every 6 weeks for Eribulin cohort. The date of each Control Visit is not determined with respect to the preceding one but with regard to time since first dose of protocol treatment (± 3 , etc. days after first dose). On each visit the following procedures are carried out:

- Assessment of vital signs (heart rate, blood pressure, temperature)
- Physical examination
- Standard 12-lead ECG for ribociclib cohort
- Assessment of adverse events (see section 11)
- Documentation of protocol treatment
- Tablet count, further supply of everolimus/ribociclib if necessary (everolimus/ribociclib cohort only)
- Pregnancy test (eribulin cohort only)
- Assessment of concomitant medication (denomination, start date/end date, specification if ongoing, dosage, route)
- Blood sampling for hematology and chemistry. Analyses are to include the parameters given in TABLE 26 below.
- Assessment of quality of life by means of the EORTC QLQ-C30 and EORTC QLQ-BR23 questionnaires
- Assessment of survival

Hematology	
 - Hemoglobin - Hematocrit - Red blood cell count - Differential white blood cell count - Platelet count
Biochemistry	
 - Total and direct bilirubin - ALT/AST - GGT, AP, and LDH (ribociclib cohort only) - Serum creatinine - Albumin - BUN or urea - Sodium, potassium, calcium, phosphorous (ribociclib cohort only) - Fasting cholesterol and triglycerides (everolimus/cohort only) - Fasting glucose (everolimus cohort only) - Potassium and Magnesium (eribulin cohort only)

Table 26: Standard hematology and biochemistry

During treatment CTC determination should be performed with **Analysis Kit** at week 3 - 4 and 9 -12 (that means for the eribulin cohort after cycle 1 and 3) only in patients who have given informed consent for translational medical investigations (**TraFo-Project**).

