APPENDIX II – PATIENT EVALUATION FLOW SHEET

Visits	Screening Visit	Inclusion Visit	Control Visits	Conclusion Visit of Treatment Period	Follow-up Assessments
Time	≤ 21 days prior to end of Inclusion Visit	≤ 21 days after Screening Visit	Every 3 to 4 weeks (Everolimus/ribociclib cohort) and every 6 weeks (eribulin cohort)	12 months after first dose or at premature termination of protocol treatment	2 to 4 weeks after Conclusion Visit, then q 3 months
Periods	Pre-Treatment Evaluation Period		Treatment Period		Follow-Up Period
Informed consent - part 1 in blood sampling for CTC count and HER2 status on CTC ¹	X				
Informed consent - part 2 in study participation ¹		X			
Informed consent - part 3 in blood sampling for translational medical investigations ^{1,2}		X			
Allocation of the patient identification number	X				
Demography (YOB)*	X				
Date of primary tumor diagnosis*	X				
Information on primary breast cancer (TNM*, histology*, grading*, localisation**, surgery**)	X				
Information on metastases (date of diagnosis*, localization*, surgery**)	X				
HER2 status on primary tumor tissue and/or biopsies from metastatic sites	X				
Hormone receptor status on primary tumor tissue and/or biopsies from metastatic sites ⁴	X				
Adjuvant/Neoadjuvant Therapy**	X				
Number of prior chemotherapy lines for metastatic disease*, type of therapies for metastatic disease**	X				
Blood sampling for CTC within the clinical trial	X ⁵ Screening Kit		X ¹⁷ (every 12 weeks) with Analysis Kit everolimus/ribociclib cohort only	X ¹⁷ (Analysis Kit)	
Blood sampling for translational medical investigations	X ⁶ (part of Screening Kit)	X ¹⁹ Analysis Kit	X ¹⁹ (Analysis Kit) Only at visits week 3-4 and 9-12		
Patient height + weight		X			
Medical/surgical history		X			
Concomitant diseases		X			
Ongoing toxicities attributed to prior anti-cancer therapies ³		X			
Prior anticancer medication, other relevant prior medication		X			
Concomitant medication		X	X	X	X

Visits	Screening Visit	Inclusion Visit	Control Visits	Conclusion Visit of Treatment Period	Follow-up Assessments
Documentation of and check for compatibility of planned endocrine therapy in combination with everolimus		X			
Protocol treatment		X	X	X ¹⁶	
Vital signs (heart rate, blood pressure, temperature)		X	X	X	
Physical examination		X	X	X	
Adverse Events		X	X	X	X
Hematology ⁷		X ^{9, 20}	X ^{20, 21}	X	
Biochemistry ⁸		X ⁹	X ²⁰	X	
Pregnancy test (eribulin cohort only)		X ⁹	X	X	

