- ¹⁶ Documentation of end of protocol treatment and documentation of planned therapy after end of protocol treatment
- ¹⁷ CTC count with Analysis Kit should be performed every 3 months (not in the eribulin cohort). Generally treatment response evaluation should be performed together with the determination of CTCs as part of clinical trial. CTC count at conclusion visit (i.e. end of treatment or progress) should be performed for both cohorts with Analysis Kit.
- ¹⁸ Tumor markers are assessed on each tumor evaluation: CA15-3 is mandatory, CA125 and CEA are optional
- ¹⁹ Blood sampling with Analysis Kit as part of translational research projects (only with informed consent part 3) at week 3 - 4 and at week 9 – 12 (in the eribulin cohort CTC count should be performed after cycle 1 and 3, in the everolimus/ribociclib cohort CTC count should be performed in the mentioned period).
- ²⁰ Ribociclib-cohort:
ECG: Cycle 1 d14, and at the beginning of the second cycle, and as clinically indicated.
Liver Function Test (LFT): monitor LFTs every 2 weeks for the first 2 cycles, at the beginning of each subsequent 4 cycles, and as clinically indicated.
- ²¹ Eribulin-cohort: monitoring of complete blood counts should be performed on all patients prior to each dose of eribulin.

*Data must be obtained before screening

**Patients may be screened without obtaining this additional information. Documentation of these data will be reimbursed additionally.

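### The eribulin CTC endpoint is defined at weeks 6 and 12, but section 9.1 and the flow sheets draw blood after cycles 1 and 3 (weeks 3 and 9); section 2.10.3.3 gives a third, TNBC-only schedule

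*Protocol*

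**What the plan says.** Protocol section 1.2.2 (Eribulin cohort), repeated in the synopsis, defines the CTC dynamics endpoint as "changes in CTC counts from baseline numbers (start of treatment) to first (6 weeks) and second (12 weeks) control visit", together with the time of progression or end of treatment. These time points match the control visits, which section 9.1 sets at "every 6 weeks for Eribulin cohort".

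The instructions that tell sites when to draw blood are different:

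- Synopsis, Control Visits: "Blood sampling with Analysis Kit in week 3-4 and 9-12 only in patients who have given informed consent - part 3".
- Section 9.1 gives the same weeks and explains them: "that means for the eribulin cohort after cycle 1 and 3) only in patients who have given informed consent".
- Appendix II, row on translational blood sampling: "Only at visits week 3-4 and 9-12".
- Appendix II, footnote 19: "in the eribulin cohort CTC count should be performed after cycle 1 and 3". The German flow sheet in Appendix I repeats both the row and this footnote.
- Appendix II, footnote 17, takes eribulin out of the regular in-trial count: "CTC count with Analysis Kit should be performed every 3 months (not in the eribulin cohort". The same footnote, and section 9.1, keep a CTC count at the conclusion visit for both cohorts.

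A third statement is in section 2.10.3.3, the 53BP1 project, which concerns triple-negative (TNBC) patients: "Additional blood samples will be collected 0, 6, and 12 weeks after treatment start with Eribulin". That section also says CTCs will be enumerated in these samples.

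**The concern.** The endpoint and the sampling schedule name different weeks, and timing cannot be repaired at the analysis stage: no analysis plan can supply a week-6 count that was never drawn. Sites work from the visit list and the flow sheet, so the schedule written there will determine which data exist.

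Section 2.7.3 suggests that longitudinal CTC assessment may help explain why eribulin's OS benefit and PFS benefit differ in triple-negative patients, and section 2.10.3 makes CTC prevalence and number the main focus of the DIVb translational programme. The endpoint definition also does not say that its on-treatment values exist only for patients who give the optional part-3 consent.

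**Working it through.** **Inputs.** Cycle length 21 days (8.4.1.9). Draw windows weeks 3-4 and 9-12, equated with after cycles 1 and 3 for eribulin (9.1; Appendix II, footnote 19). Endpoint weeks 6 and 12 (1.2.2). Projected DIVb population: about 270 TNBC patients among about 390 eligible, and about 120 enrolled (15.3).

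**Cycle calendar.** The end of cycle k is week 21k/7 = 3k:

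| After cycle | Week |
|---|---|
| 1 | 3 |
| 2 | 6 |
| 3 | 9 |
| 4 | 12 |

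This reproduces the protocol's own link between cycles 1 and 3 and the start of the two windows. The endpoint weeks correspond to cycles 2 and 4.

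**Endpoint weeks against the windows.**

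- Week 6 lies in neither window: it is 6 − 4 = 2 weeks after the first closes and 9 − 6 = 3 weeks before the second opens.
- Week 12 is the last point of the 9-12 window, but 12 − 9 = 3 weeks later than after cycle 3. The window permits it; the cycle instruction does not.
- The 3-monthly in-trial count could have supplied week 12 without part-3 consent, but eribulin is excluded from it.
- The Appendix II row refers to visits at weeks 3-4, although the eribulin control visits in the same table are 6-weekly. A site reading the visit column and a site reading footnote 19 could therefore draw at different times.

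**Who has a week-6 draw planned anywhere.** Only section 2.10.3.3 plans one, and only for TNBC patients. Assuming the same inclusion fraction in both subgroups:

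- TNBC: 120 × 270/390 = 83.1, about 83 patients (69%).
- Hormone-receptor positive: 120 × 120/390 = 36.9, about 37 patients (31%).

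The protocol rounds its inputs. Unrounded, TNBC is 910 × 0.30 = 273 and hormone-receptor positive with chemotherapy indication is 910 × 0.70 × 0.20 = 127.4. The split of 120 is then about 82 and 38. The 82 to 83 is a ceiling, before consent and early progression are taken into account.

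**The case against.** The strongest case on the other side has four parts.

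1. **Section 2.10.3.3 is itself a collection instruction.** It plans week-0, week-6 and week-12 samples with CTC enumeration. A reader might infer from section 9.1 and the flow sheets that no eribulin patient has a week-6 sample and that the endpoint cannot be computed at all. The documents do not support that: a week-6 change could be computed in consenting TNBC patients if 2.10.3.3 is followed. What stands is that these draws appear in neither 9.1 nor the flow sheets, so the protocol holds two incompatible schedules.
2. **The conclusion-visit count covers all patients in both cohorts.** This stands. The progression or end-of-treatment component of the endpoint is intact.
3. **Week 12 lies inside the stated window.** True, and the conflict at that time point is only with the cycle-3 instruction. Week 6 has no such rescue.
4. **The stakes are modest.** Section 15.2 calls all secondary analyses exploratory and describes CTC counts over time descriptively and with generalized linear mixed models, which can use whatever times are sampled. Section 2.7.3 says only that longitudinal counts could be useful, and names before treatment, during treatment and progression, not week 6. This also stands: it limits the consequence but does not remove the contradiction. Nor do the documents show that counts from weeks 3 and 9 would be reported as week-6 and week-12 values.

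**Conclusion.** The point holds as an internal contradiction. Under section 9.1 and the flow sheets, the baseline-to-week-6 change in the DIVb endpoint cannot be obtained. The week-12 change is reachable only at the edge of the 9-12 window and against the instruction to draw after cycle 3. Section 2.10.3.3 would supply both weeks for TNBC patients alone, leaving about 37 of 120 patients with no week-6 draw planned in any section. That figure rests on the protocol's recruitment projection and on equal inclusion fractions in the two subgroups; the contradiction itself rests on neither.

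The consequence is limited to one exploratory secondary endpoint. It should still be corrected, because the missing time point cannot be recovered later.

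**What to change.** Use one DIVb schedule throughout. Either option works:

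- **Move the draws.** Set the eribulin Analysis Kit draws at the existing 6- and 12-week control visits (after cycles 2 and 4). Change the synopsis visit list, section 9.1, the Appendix II row and footnote 19, and the matching row and footnote in the German flow sheet. The synopsis line and the flow-sheet rows are shared with the everolimus/ribociclib cohort, so word them by cohort to leave the DIVa timing unchanged.
- **Move the endpoint.** Restate the DIVb endpoint in the synopsis and section 1.2.2, and the sampling times in section 2.10.3.3, as after cycles 1 and 3. Replace the reference to weeks 3-4 visits in the flow sheets with wording that fits eribulin, and settle whether the second draw is at week 9 or anywhere in weeks 9-12.

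With either option, state that the on-treatment change scores apply to patients with part-3 consent, and report the actual sampling week.

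The cost is wording. The number of draws in the operative schedule stays at two, and the first option uses visits that already take blood. Treatment is not affected.

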2 BACKGROUND INFORMATION AND RATIONALE

2.1 Metastatic Breast Cancer

With an estimated 1.38 million new cancer cases diagnosed in 2008 (23% of all cancers), breast cancer is by far the most frequent cancer among women. Incidence rates vary from 19.3 per 100,000 women to 89.7 per 100,000 women, and are considerably higher (greater than 80 per 100,000) in developed regions of the world (except Japan) as compared to most of the developing regions (less than 40 per 100,000). Mortality rates range from approximately 6-19 per 100,000, and breast cancer ranks as the fifth cause of death from cancer overall (458 000 deaths), still being the most frequent cause of cancer death in women. Despite significant improvements in early diagnosis and treatment of breast cancer, about 40% of women with breast cancer will relapse and ultimately die of metastatic disease. Recurrent or metastatic breast cancer (MBC) is an incurable malignancy with a median survival of 24 – 30 months or less. Treatment for MBC is palliative, and the goals are to reduce tumor size, to slow down progression and metastasis, to reduce complications such as fatigue, bone fracture and hypercalcemia, and to increase quality of life. Although initial treatments did not achieve these goals, in the last decade a number of studies using new contemporary agents have shown promising results with increased response rates and benefits in terms of prolonged progression-free and overall survival.

2.2 Hormon-Receptor positive Breast Cancer

The presence of estrogen receptor (ER) and/or progesterone receptor (PgR) is one of the most important predictive and prognostic markers in human breast cancers. Approximately 70% of all invasive breast cancers are positive for ER and/or PgR expressions at the time of diagnosis. Consequently, anti-estrogen therapies that antagonize ER functions (such as tamoxifen) or inhibit estrogen production (e.g. aromatase inhibitors [AIs]) have been extensively developed in oncology (Jensen and Jordan 2003, Smith and Dowsett 2003). Deprivation of estrogenic signaling with the anti-estrogen tamoxifen has been the main form of hormonal treatment for over 30 years. Tamoxifen is indicated for the treatment across the whole continuum of breast cancer, ranging from risk reduction for women with increased risk of breast cancer, as an adjuvant treatment and also for metastatic disease. While therapies interfering with ER functions such as tamoxifen have significantly contributed to mortality reduction in advanced breast cancer (ABC) patients, at best 50-60% of ER positive patients respond to anti-estrogen therapy. Consequently, a number of aromatase inhibitors (AI) that reduce peripheral estrogen synthesis have been developed for the treatment of ABC. The AIs block the conversion of androgens to estrogens, which is the primary way estrogens are produced in post-menopausal women. At present, third generation aromatase inhibitors have been approved for use in postmenopausal women with hormone receptor positive BC after tamoxifen. The third generation AIs can be broadly classified into two groups: non-steroidal aromatase inhibitors (NSAI), mainly letrozole (Femara®) and anastrozole (Arimidex®) and steroidal aromatase inactivators, represented by exemestane (Aromasin®).

2.3 Circulating tumor cells

Hematogenous tumor cell dissemination is a crucial step in tumor progression, and blood-derived metastases account for the majority of breast cancer-related deaths. Cells that are able to disseminate into the circulation are of biologic relevance as potential founder cells for new metastases, and CTC detection and characterization have already improved our understanding of the complex process underlying tumor cell dissemination and metastatic progression in breast cancer.

Previous research has shown that CTCs ($\geq 1 / 7.5$ ml blood) are present in 65-85% of patients with MBC (Fehm et al. 2010, Botteri et al. 2010, Müller et al. 2012, Pierga et al. 2012), and five or more CTCs are detected in about 40-50% of MBC patients (Cristofanilli et al. 2004, Budd et al. 2006, Fehm et al. 2010, Müller et al. 2012, Pierga et al. 2012). There is good evidence that CTCs detected in the peripheral blood of patients with MBC can both provide prognostic information (Budd et al. 2006, Cristofanilli et al. 2005, Hayes et al. 2006, Giuliano et al. 2011, Giordano et al. 2012, Wallwiener et al. 2013) and indicate therapy success (Liu et al. 2009, Pierga et al. 2012).

The FDA approved standardized and semi-automatic CellSearch™ system (Veridex, LLC, USA) will be used for capture, isolation and enumeration of CTCs. The method has been described in detail in a validation study by Riethdorf et al. 2007, and is now routinely being used in the laboratories responsible for conducting the translational research program in the DETECT IV study. Briefly, blood samples are collected into special CellSave tubes, centrifuged to separate solid blood components from plasma, and then placed in the CellTracks® AutoPrep® System. Using ferrofluid nanoparticles with antibodies that target epithelial cell adhesion molecule (anti-EpCAM), CTCs are magnetically separated from the other cells in the blood. CTCs are then stained with the fluorescent nucleic acid dye 4',6-diamidino-2-phenylindole (DAPI), cytokeratin monoclonal antibodies (specific to epithelial cells) and a

monoclonal antibody to identify CD45 (a marker specific to leukocytes) to be able to distinguish epithelial cells from leukocytes. Cells are put in a magnet cartridge that applies a magnetic force pulling the cells to a single focal depth. The cartridge containing stained CTCs is placed into the CellTracks Analyzer II® for scanning, and the system presents tumor cell candidates (nucleated cells lacking CD45 and expressing cytokeratin) to an operator for final review. HER2 expression of CTCs is characterized within the CellSearch™ system by the addition of a fluorescein-labeled anti-HER2 antibody (CellSearch™ tumor phenotyping reagent HER2; Veridex, LLC), as described previously (Riethdorf et al. 2010).

